Following the two weeks of CREMA data collection, a laboratory session will be conducted to investigate responses to acute dosing of oxytocin (versus placebo) in context of controlled evaluation of stress reactivity and smoking behavior. Prior to the session, participants will abstain from smoking for 12 hours and provide a salivary sample for measurement of stress and sex hormone (cortisol, estradiol, progesterone, and testosterone) levels. Participants will receive a double blind intranasal dose of oxytocin or placebo and will then be exposed to the Trier Social Stress Test (TSST). Measures collected at multiple time points during the laboratory session will include subjective craving, stress, and negative emotion as well as heart rate, blood pressure, skin conductance, and cortisol. Immediately following the TSST, participants will complete a smoking resistance task (SRT) in which they will receive a monetary reward for every 5-min period they can resist smoking. After completing the SRT, participants will be allowed to smoke freely during a one-hour ad libitum smoking period (ASP), with smoking topography assessed via a portable device.

Aim 1: Evaluate gender and sex hormone influences on reactivity to stressful and smoking-related cues presented, via CREMA, in the natural environment of smokers.

Hypothesis 1: Female smokers will be more reactive (craving ratings) than male smokers to stressful and smoking-related cues presented in the natural environment.

Hypothesis 2: Among female smokers, estrogen to progesterone ratio will be positively related to reactivity (craving ratings) to stressful and smoking-related cues presented in the natural environment.

Aim 2: Evaluate gender, sex hormone, and oxytocin administration influences on stress, craving, and smoking behavior response to a laboratory-based stressor task (TSST).

Hypothesis 1: Female smokers will evidence greater subjective stress, craving, and smoking behavior (e.g., shorter latency to smoke during the SRT and greater number of puffs during the ASP), but less neuroendocrine reactivity (cortisol), to the TSST than male smokers.

Hypothesis 2: Oxytocin, relative to placebo, will attenuate subjective stress, craving, and neuroendocrine responses to the TSST.

Hypothesis 3: Among female smokers, estrogen to progesterone ratio will be positively related to craving reactivity during the TSST.

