Enrolled participants will return for a training visit, during which they will gain mastery of saliva sample collection and storage, personal digital assistant (PDA; iPhone) operation, and CREMA procedures.

C3e. Natural Environment Procedures.

CREMA Assessment. Participants will carry a PDA for two weeks (Days 1-14). They will be instructed to keep the PDA with them at all times. Auditory alarms will alert participants to complete four, randomly scheduled cue-reactivity/CREMA sessions per day (session duration = 3-4 min.). Alarms will be distributed over a 12-hour period, divided into four, 3-hr blocks with a minimum time of 30 minutes between alarms/CREMA sessions. Each CREMA session will contain two trials and each trial will consist of one picture cue presentation. There will be three types of picture cues that differ based on content: stressful (e.g., stress-inducing images from the standardized International Affective Picture System [IAPS; Libkuman et al., 2007; Rehme et al., 2009]), smoking (e.g., lit cigarettes, people smoking, etc.) and neutral (e.g., pencils, scissors, etc.). Thus, each of the four daily CREMA sessions will contain two picture cues from one or a combination of these three categories.

At the start of each CREMA session, participants will be asked to finish their cigarette if they were smoking, then provide craving and mood ratings, and answer questions about distractibility, etc. (see Section C3g. Instruments/Measures). Next, a photograph will be presented and the participant will be instructed to look at it carefully. Each picture cue will appear only once during the study. An alarm will sound at the end of each trial, after which participants will complete a post-cue assessment consisting of the Craving Questionnaire, mood items, and ratings of how carefully they looked at the photograph and their distraction level during each trial. CREMA sessions will present the pictures for 10 seconds.

Participants will be prompted for four CREMA sessions per day on Days 1-14, and will thus complete a maximum of 56 CREMA sessions. To encourage CREMA session completion, participants will be compensated \$1.25 for each completed session (see Participant Compensation, Section C3h). Previous studies employing this incentive strategy have reported 90% CREMA completion rates (Gass, et al., 2011; Warthen & [name], 2009a; Wray, et al., in press).

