This study is powered to test the hypothesis that non-cigarette-deprived females will be more reactive to smoking cues than males, as measured in the natural environment of smokers via CREMA technology. However, the sample size obtained for this is adequate to test all the four hypotheses with at least 80% power. The justifications for the power calculations are as follows. A recent study (Heishman, et al., 2010) found that non-cigarette-deprived females responded to smoking cues with 10% greater craving than males (i.e., 10-unit difference on a 100-mm VAS), with this difference corresponding to an effect size of $d = 0.7$. Since the proposed design intends to assess gender differences in a non-laboratory setting, we have reduced the expected effect size by 30% to 0.50. Based on the four-item subscale of the QSU (cf., Warthen & [name], 2009b) to be used in the proposed study, a comparable detectable gender difference would be 0.45 ($sd=0.9$). Accounting for the multiple correlated measures within each participant (i.e., reactivity will be measured multiple times daily for 14 days using CREMA) through a between-observation correlation (autocorrelation) of 0.70, a sample of 96 females and 48 males is necessary to achieve 90% power (with a two sided type I error rate of 0.05) to detect the minimum relevant effect size of $d=0.50$. It is estimated that up to 20% of the participants may be lost before completion of the study.

Assuming 144 participants complete all study procedures (accounting for 20% dropout), we will also have 80% power with a type I error of 0.05 to detect a minimum effect size of $d=0.50$ between females and males in stress and craving response to the TSST and similarly between the oxytocin and placebo groups.

C3j. Data Management & Statistical Analysis.

Data Management

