All paper-based assessments will be entered into SPSS databases using dual data entry methods for 20% of cases. Semi-annual database management and data integrity audits will be conducted. Hormone and cortisol data will be obtained from MUSC's CTSC in pre-formatted data files. HR and SC data will be acquired via specialized software and hardware (Biopac Systems, Inc.) interfaced with a computer. Standardized file formats will facilitate the rapid determination of summary values to be used for analysis purposes. The CREMA data will be automatically uploaded to a server on a daily basis and will be stored in a standard file format (to be determined in collaboration with [name] (Founder of Slicker Interactive & CREMA software developer). All data will be de-identified using participant ID number.

Statistical Analysis

Univariate descriptive statistics and frequency distributions will be calculated for all variables. Departures from distributional assumptions for the proposed parametric methods will be identified and appropriate transformations of the data will be applied or alternative procedures (semi/non parametric methods) will be employed. Baseline values for demographic, clinical, and other prognostic variables will be compared for imbalance across gender and treatment groups. These analyses will identify potential confounding variables to be used as covariates in subsequent analysis.

Aim 1: Hypothesis 1 - To test the overall hypothesis that females will be more reactive than males to stressful and smoking-related cues presented in the natural environment, a linear mixed effects model will be employed. The dependent variable will be craving and the primary independent variable will be gender. In the modeling process, within-subjects factors of stimulus type (active and neutral cues) and presentation order will also be included.

Hypothesis 2 - To test the hypothesis that the estradiol to progesterone ratio will be positively related to cue-elicited craving in the natural environment, salivary hormone levels and craving in response to the CREMA picture cues will be assessed over 14 days. Hormone curves do not behave in a linear fashion, but may, in the example of progesterone, behave in a quadratic fashion preceding menses and a linear fashion following

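### Aim 1 Hypothesis 1 is about cue reactivity, but the only term its model singles out is gender on craving level; no gender-by-cue-type test is named

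*Combined protocol and SAP*

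**What the plan says.** The Specific Aims state Hypothesis 1 of Aim 1 as: "Female smokers will be more reactive (craving ratings) than male smokers to stressful and smoking-related cues presented in the natural environment". Section C3j tests it with a linear mixed effects model. "The dependent variable will be craving and the primary independent variable will be gender"; in addition, "within-subjects factors of stimulus type (active and neutral cues) and presentation order will also be included". The section names no interaction for Aim 1. The only interaction in the plan is gender by medication in Aim 2, as a secondary analysis.

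Section C3e describes three cue types (stressful, smoking, neutral), two single-picture trials per session and at most 56 sessions. It does not give the share of trials for each cue type. At the start of each session participants finish any cigarette, "then provide craving and mood ratings, and answer questions about distractibility"; craving is rated again after each cue.

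Section C3i sizes the study on this hypothesis, for smoking cues only: 96 women and 48 men for 90% power at two-sided 0.05, with d = 0.50 (0.45 points, SD 0.9) and a between-observation correlation of 0.70. The effect comes from a laboratory study in which "females responded to smoking cues with 10% greater craving than males"; no neutral-cue comparison is mentioned there.

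**The concern.** Reactivity is a change or a contrast: craving after an active cue compared with craving after a neutral cue, or with craving before the cue. In a model with gender and stimulus type as additive terms, the gender coefficient is neither. It is the female-minus-male difference in craving level over all trials. Adding stimulus type as a factor removes the average cue effect, which is the same for both sexes in that model, and leaves gender as a level difference.

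Two errors become possible. If women simply crave more through the day, the test supports the hypothesis with no difference in reactivity. If women do react more to active cues, the neutral trials dilute the effect.

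The team's own work in section C1 isolates reactivity: the earlier gender study adjusted for the response to neutral cues, and the ongoing study used post-cue minus pre-cue craving. The plan for Aim 1 carries over neither, although both ingredients are collected.

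The two-level stimulus factor also merges stressful with smoking cues. The hypothesis names both and the sample size concerns smoking cues. The earlier gender study found a gender difference for the stress script but no significant one for smoking cues. The wider set of studies cited in C1 is more favourable on smoking cues (five of eight found women more craving-responsive).

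**Working it through.** **Inputs from the documents.** 96 women and 48 men, two-sided 0.05, d = 0.45/0.9 = 0.50, correlation 0.70 (C3i); 56 sessions × 2 trials = 112 trials at most (C3e).

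**Assumptions.** Exchangeable correlation. In units of the 0.9 SD, between-person variance is then 0.70 and within-person variance 0.30. The active share of trials is varied because it is not stated. Between-person variation in reactivity is zero unless noted.

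**The plan's own figure.** The variance of a person's mean over m ratings is (1 + (m − 1) × 0.70)/m.
- m = 1: 1.00, power about 80%.
- m = 5: 0.76, power 90.05% by the normal approximation, which returns exactly 96 and 48.
- m = 14 to 112: about 91% to 92%.

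So 90% is reproduced to within about two points. The calculation is for a between-group difference in mean craving, which is what the gender coefficient measures.

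**Gender coefficient under two scenarios.** With 112 trials the variance is 0.70 + 0.30/112 = 0.7027, root 0.838. The group-size factor is √(96 × 48/144) = √32 = 5.657. The noncentrality is d × 5.657/0.838, on 142 degrees of freedom.

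*(a) Women higher on every cue, reactivity identical.*
- d = 0.5: noncentrality 3.37, significant 92% of the time.
- d = 0.2: noncentrality 1.35, significant 27% of the time.

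*(b) True difference of 0.50 SD (0.45 points) on active cues only.* The averaged effect is 0.50 × active share.

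| Active share | Averaged d | Noncentrality | Power |
|---|---|---|---|
| 50% | 0.25 | 1.69 | 39% |
| two-thirds | 0.333 | 2.25 | 61% |
| 75% | 0.375 | 2.53 | 71% |
| 80% | 0.40 | 2.70 | 76% |

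Allowing reactivity to vary between people lowers these figures moderately. With an assumed slope variance of 0.1 to 0.3 and two-thirds active trials, (a) at d = 0.5 becomes about 90% to 87%, and (b) becomes 59% to 54%.

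The sign can also mislead. If women are 0.5 SD higher on neutral cues but 0.25 SD less reactive, the averaged effect is 0.5 − 0.25 × 2/3 = 0.333. In simulation (slope variance 0.1) the gender test supports the hypothesis in 58% of trials, while the gender-by-cue contrast finds the opposite direction in 99%.

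**The reactivity contrast itself.** Let s be the between-person SD of reactivity in the same units. With about 37 smoking and 37 neutral trials, the variance is s² + 0.30 × (1/37 + 1/37) = s² + 0.016. For a reactivity difference of d = 0.50:
- s = 0.775 (0.70 points; 0.775² ≈ 0.6 = 2 × (1 − 0.70), one active/neutral pair): noncentrality 2.828/√0.617 = 3.60, power 95%.
- s = 0.9 (0.81 points): 2.828/√0.826 = 3.11, power 87%.
- s = 1.0 (0.90 points): 2.828/√1.016 = 2.81, power 80%.

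The documents do not give s.

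**The case against.** The strongest reply is that C3j under-specifies the test and does not choose the wrong one. It introduces the hypothesis as one of reactivity, puts a neutral level in the model, and never uses the term main effect for Aim 1; that term appears only for Aim 2. A neutral level has little purpose except as a comparator, so the team may have meant to fit the interaction. This stands as a limit on the point: a reader might infer that the plan deliberately adopts the gender main effect, and the text does not say so. But gender is the stated primary term and no other test is named. Leaving the interaction unstated permits a choice after the data are seen between two tests that can disagree.

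It can also be said that the documents do not fix one definition of reactivity: the hypothesis refers only to craving ratings, and the sample size to craving after smoking cues. That is true, and it is part of the gap. Analysing active-cue ratings alone would not close it, because craving after an active cue still mixes level with reactivity.

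A reader might further infer that the sample is too small for the reactivity contrast. The documents do not support that: the contrast keeps about 80% to 95% power at d = 0.50 for reactivity SDs of 1.0 down to 0.775.

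Two more caveats stand. The tonic differences in scenario (a) are hypothetical, since the documents report no tonic gender difference in craving. And pooling active cues can be defended for what C3j calls the overall hypothesis, though it does not match a sample size stated for smoking cues.

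**Conclusion.** The point holds as a mismatch between the hypothesis and its stated test. Followed literally, the analysis estimates a gender difference in craving level. It could support the hypothesis in about 92% of trials with no reactivity difference (tonic d = 0.5; 27% at d = 0.2), and would detect the planned difference, if confined to active cues, with roughly 39% to 76% power depending on the active share.

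These figures rest on 96 and 48 completers, exchangeable correlation of 0.70, 112 trials and no between-person variation in reactivity. The 90% in C3i belongs to a difference in mean craving. Power for the reactivity contrast is a separate quantity. It is probably adequate at d = 0.50 but depends on an SD that the plan does not state. Because this is the hypothesis on which the study is powered, the test should be named before analysis.

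**What to change.** In C3j, name gender by cue type as the test of Hypothesis 1, in a mixed model for post-cue craving with:
- gender, cue type at three levels (stressful, smoking, neutral) and their interaction;
- gender × (smoking versus neutral) as the primary contrast, to match C3i, and gender × (stressful versus neutral) as a separate pre-stated contrast, with the handling of the two tests stated;
- a random intercept and random cue slopes per participant, so that the contrast is judged against between-person variation in reactivity;
- session-start craving as a covariate, together with trial position, because that rating does not directly precede the second trial, and presentation order as already planned.

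Report the gender main effect only as overall craving.

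In C3i, say that the 90% was computed for a between-group difference in mean craving. Give the assumed SD of the reactivity contrast with the resulting power, and state the planned share of trials for each cue type.

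The cost is a rewording of the analysis plan and a slightly more complex model with more variance parameters. Every variable needed is already in the data collection, and no participants are added.

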Relevant Gender Differences Experience. In one of our previous SCOR studies ([name] et al., in press) we examined the effects of gender on craving and cue reactivity. We recruited female (n=37) and male (n=53) nicotine dependent smokers to participate in a multi-session laboratory study of craving and cue reactivity to smoking and stress/negative affect cues. The smoking cues consisted of a package of the participant’s preferred brand of cigarettes, which (s)he held and manipulated for 90 sec. as instructed by research staff. The stressful/negative affect cues consisted of a detailed description of a recent life event that the participant perceived as emotionally negative and stressful. Neutral control cues for the smoking cues consisted of a similar guided manipulation of a pack of pencils and an eraser while a script of a neutral or relaxing event that the participant had recently experienced served as a control for the stressful/negative affect script. Following each cue presentation, participants provided subjective ratings of stress, craving, arousal (calm vs. aroused), valence (pleasant vs. unpleasant; lower ratings indicate more unpleasant) and dominance (feeling in control vs. feeling out-of-control/submissive; lower ratings indicate feeling more out-of-control/submissive). In addition to subjective

measures, heart rate (HR) and skin conductance (SC) measures of physiological arousal were assessed at baseline and during each cue exposure. ANCOVAs were performed to assess gender differences in cue reactivity; covariates in the models were responses to neutral cues, FTND score (measure of nicotine dependence level) and order of cue presentation. Results of analyses performed on smoking cue data indicated that although women trended toward having greater stress, craving, arousal, and lower valence and dominance ratings than men, none of the differences reached significance (e.g., arousal difference, $p = .09$). Analyses of the HR/SC data indicated that (a) women trended towards greater heart rate than men ($p = .05$) but this effect was not cue specific (i.e., did not vary across smoking vs. neutral cue type), and (b) SC level

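### Aim 1 Hypothesis 1 concerns reactivity to active cues, but C3j names gender as the primary effect on craving and no gender-by-stimulus contrast, so on its plain reading the test pools active and neutral pictures

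*Combined protocol and SAP*

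**What the plan says.** Specific Aims, Aim 1 Hypothesis 1, reads: "Female smokers will be more reactive (craving ratings) than male smokers to stressful and smoking-related cues presented in the natural environment". C3i says the study is "powered to test the hypothesis that non-cigarette-deprived females will be more reactive to smoking cues than males". Its inputs are a difference of 0.45 with SD 0.9 (d = 0.50), a between-observation correlation of 0.70, two-sided 5% error, and 96 women and 48 men for 90% power.

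C3j, Aim 1 Hypothesis 1, specifies a linear mixed model: "The dependent variable will be craving and the primary independent variable will be gender". It adds that "within-subjects factors of stimulus type (active and neutral cues) and presentation order will also be included". The paragraph mentions no gender-by-stimulus term, active-minus-neutral contrast, change from pre-cue craving or restriction to active cues. It also gives no random-effects structure.

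C3e describes three picture categories (stressful, smoking, neutral) and says "each of the four daily CREMA sessions will contain two picture cues from one or a combination of these three categories". The share of neutral trials is not given. Participants "will thus complete a maximum of 56 CREMA sessions", with two trials in each. At the start of a session they finish any cigarette, "then provide craving and mood ratings, and answer questions about distractibility, etc". That pre-cue rating has no role in the Hypothesis 1 model.

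C1 describes the team's earlier laboratory study of gender: "covariates in the models were responses to neutral cues, FTND score" and cue order.

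**The concern.** Reactivity is a difference between the response to an active cue and the response to a control. A gender effect in a model that holds both kinds of trial, with stimulus type as an additive factor, is a difference in average craving level. The two can part company in both directions:

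- If women crave more whatever the picture, the gender term picks this up and the result would be reported as greater reactivity.
- If women differ only on active cues, the neutral trials dilute the difference.

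This is the hypothesis on which the study is powered. A significant result would not by itself support the conclusion, and a null result could reflect dilution. C1 shows that the team knows the distinction: besides adjusting for neutral-cue responses, it reports a heart-rate trend by gender and notes that it was not specific to the cue.

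**Working it through.** **Inputs.** From C3i: difference 0.45, SD 0.9, correlation 0.70, 96 women and 48 men, two-sided 0.05. From C3e: at most 56 × 2 = 112 trials per person. Assumed, because the documents are silent: the number of measures m behind the power figure, exchangeable correlation, the neutral share, the background gender gap, and the between-person SD of reactivity.

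**1. The plan's own figure.** The SD of a person's mean is 0.9 × √[(1 + (m − 1) × 0.70)/m]. The SE of the gender difference is that SD × √(1/96 + 1/48) = SD × 0.1768. Power is from the noncentral t.

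- m = 6: factor 4.5/6 = 0.75; SD 0.779; SE 0.138; 0.45/0.138 = 3.27; power 0.900.
- m = 112: factor 78.7/112 = 0.703; SD 0.754; SE 0.133; 0.45/0.133 = 3.37 (unrounded SE); power 0.918.

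So 96/48 for 90% reproduces with a handful of exchangeable measures, provided the full 0.45 reaches the tested term.

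**2. Pooled gender effect under two truths.** The pooled effect is the background gap plus (active share × reactivity difference). The last column runs from m = 6 to m = 112.

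| Truth | Pooled effect | Probability of significance |
|---|---|---|
| 0.45 on active cues only, 1/3 neutral | 0.45 × 2/3 = 0.30 | 58–61% |
| 0.45 on active cues only, 1/2 neutral | 0.45 × 1/2 = 0.225 | 37–39% |
| No reactivity difference, gap 0.2 SD | 0.2 × 0.9 = 0.18 | 25–27% |
| No reactivity difference, gap 0.3 SD | 0.3 × 0.9 = 0.27 | 50–52% |

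**3. The contrast.** A simulation of 20,000 runs used 67 active and 34 neutral trials per person, which is about 90% of 112. With a 0.27-point background gap and no reactivity difference, the gender-by-stimulus contrast rejected about 5% of the time, at reactivity SD 0.6 and at 0.9. With a true reactivity difference of 0.45 and a background gap of 0.27 the other way, at reactivity SD 0.6, the pooled test was significant in about 5% of runs and the contrast in about 98.5%.

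**4. What the contrast can detect.** The variance of one person's active-minus-neutral contrast is τ² + 0.243 × (1/75 + 1/37) = τ² + 0.0098. Here 0.243 = 0.81 × (1 − 0.70), 75 and 37 are the 112 trials split at an assumed one third neutral, and τ is the between-person SD of reactivity. The detectable difference at 90% power is (1.96 + 1.28) × √(τ² + 0.0098) × 0.1768.

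| τ (assumed) | SE | Detectable difference |
|---|---|---|
| 0.3 | 0.056 | 0.18 |
| 0.6 | 0.108 | 0.35 |
| 0.9 | 0.160 | 0.52 |

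At τ = 0.9, power for 0.45 is Φ(0.45/0.160 − 1.96) = Φ(0.85), about 80%.

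**The case against.** The best defence is that C3j never calls the Aim 1 test a main effect; that term is used only for Aim 2. The Aim 1 paragraph opens by saying that the model tests whether women are more reactive. A factor with active and neutral levels is naturally there to be contrasted, and the earlier study's adjustment for neutral cues suggests the same intention. A factorial model may well contain the interaction. The hypothesis also glosses reactivity as craving ratings, and C3i takes its effect size from a gender difference in craving in response to smoking cues.

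Much of this stands. A reader might infer that the plan expressly specifies the wrong test. It does not: it leaves the tested contrast unnamed, and the pooled gender effect is the plain reading of what is written. The defence does not close the gap, though. Gender is the only effect given primary status. If an interaction were fitted with neutral as the reference level, the gender coefficient would be the gap on neutral pictures, so the contrast would still have to be named. The gloss identifies the rating scale; it does not explain why ratings after neutral pictures should count toward reactivity.

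Three further inferences fail. The 90% cannot be said to refer to craving level, because C3i ties it to reactivity and never says which quantity has SD 0.9. The contrast cannot be called comfortably powered, because that depends on a reactivity SD that the documents do not give. And no error inflation from omitting a random stimulus effect can be charged to the plan, which gives no random-effects structure for this model.

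**Conclusion.** The concern holds as a mismatch between the hypothesis and the test as written. Followed literally, the Aim 1 Hypothesis 1 analysis compares overall craving between women and men. Power for a purely cue-specific 0.45-point difference would then be about 58–61% or 37–39%, not 90%. A background gap of 0.2 or 0.3 SD would be taken for reactivity about 25–27% or 50–52% of the time.

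The sizes depend on the assumed neutral share and background gap, on exchangeable correlation, and on no between-person variation in reactivity in the pooled-effect calculation. The direction of both errors does not depend on the particular values chosen. The design can serve the right contrast: at 96/48 it has about 80% power for 0.45 even at a reactivity SD of 0.9, though C3i does not show this.

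**What to change.** In C3j, state that the Aim 1 Hypothesis 1 test is the gender-by-stimulus contrast: the female-minus-male difference in active-minus-neutral craving, given for smoking cues and for stressful cues. Fit it in a mixed model with a random intercept and a random stimulus effect for each participant. Report the gender main effect only as a difference in overall craving.

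In C3i, state whether the SD of 0.9 is that of craving level or of reactivity. Then restate the power, or the detectable difference, for the contrast under a stated between-person reactivity SD and a stated cue mix. The values under step 4 of the working show how much depends on that SD.

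The cost is wording in two sections and one power restatement. No data collection changes.

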menses. Linear models may thus be inappropriate. Traditional analyses group the hormone curves based on the estimated phases of women's menstrual cycle (follicular and luteal) for the analyses. In addition to performing the data analyses using the same method, analysis will be extended to incorporate the non-linear patterns of an individual's hormone profile. This method will be based on a non-linear regression model that has two to three segments, each one of which may be either quadratic or linear (Marrie, Dawson, & Garland, 2009). The 'joint-points' at which the segments meet, which are referred to as knots, will also be treated as unknown and determined through the modeling process. After identifying the segments, regression models assessing hormone measures against the outcome (e.g., cue-elicited craving) in each segment will be assessed and the results interpreted accordingly.

Aim 2: Hypotheses 1 and 2 - To test for gender and medication (oxytocin versus placebo) effects on reactivity profiles to the TSST during the laboratory session, a linear mixed effects model in which the dependent variables of interest are craving, stress and neuroendocrine (cortisol) response, and the primary independent fixed effects are gender, treatment group, and a random subject effect will be utilized. To account for the repeated measures, a covariance pattern for the error structure (such as an AR(1)) will be considered. The primary goal of this analysis will be to determine if the response to TSST is significantly different between females and males and/or significantly different between those who received oxytocin versus placebo (main effects of gender and medication). Additionally, as a secondary analysis, the interaction between gender and medication condition will be explored.

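### The Aim 1 models do not say how the pre-cue craving rating taken at the start of every CREMA session is used, so the gender main effect compares craving level rather than reactivity

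*Combined protocol and SAP*

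**What the plan says.** C3e (CREMA Assessment) places a craving rating before the first picture of each session: "participants will be asked to finish their cigarette if they were smoking, then provide craving and mood ratings". After each trial, "participants will complete a post-cue assessment consisting of the Craving Questionnaire, mood items". On structure, "Each CREMA session will contain two trials and each trial will consist of one picture cue presentation", and participants "will thus complete a maximum of 56 CREMA sessions". Each person can therefore give up to 56 pre-cue ratings and 2 × 56 = 112 post-cue ratings, with one pre-cue rating serving two cues.

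C3i names the gender difference in CREMA reactivity to smoking cues as the powered hypothesis. It uses a difference of 0.45 with SD 0.9 (d = 0.50), a "between-observation correlation (autocorrelation) of 0.70", 96 women, 48 men, two-sided alpha 0.05 and 90% power.

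C3j, Aim 1 Hypothesis 1, is a linear mixed model for craving with gender as the main predictor, in which "within-subjects factors of stimulus type (active and neutral cues) and presentation order will also be included". For Hypothesis 2, once the hormone curve has been cut into segments, "regression models assessing hormone measures against the outcome (e.g., cue-elicited craving) in each segment will be assessed". Neither text mentions the session-start rating. Neither defines the outcome as a change or as baseline-adjusted, and no gender-by-stimulus term is listed.

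**The concern.** The Specific Aims state both Aim 1 hypotheses in terms of reactivity. A gender main effect on craving, averaged over active and neutral cues, compares how much women and men crave overall. If women carry higher background craving but respond to cues no differently, that test can still be positive. If they differ only in response to active cues, averaging over neutral cues dilutes the effect.

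The pre-cue rating is the measurement that could separate the two, and the team has used it so before. C1 describes an earlier study of 93 women in which reactivity was the post-cue minus the pre-cue score. Leaving the rating out also leaves predictable variance in the model. Starting craving will vary between sessions, because some participants will just have finished a cigarette and others will not. For Hypothesis 2, a hormone coefficient may pick up day-to-day shifts in background craving rather than response to the cue.

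**Working it through.** **1. The plan's own power.** Inputs from C3i: difference 0.45, SD 0.9, correlation 0.70, 96 and 48 participants. The number of ratings per person, m, is not given there, so it is varied. Assuming equal correlation, the variance of a person's mean relative to one rating is f = 0.70 + 0.30/m. With 1/(1/96 + 1/48) = 32, the standardised effect is 0.50 × √32 / √f = 2.828/√f, and power = Φ(2.828/√f − 1.96).

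- m = 5: f = 0.760, power 90.05%
- m = 10: f = 0.730, power 91.2%
- m = 14: f = 0.721, power 91.5%
- m = 112: f = 0.703, power 92.1%

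The stated 90% is reached without the pre-cue rating.

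**2. Gain from removing session-to-session swing.** In this formula all within-person variance is 0.30/m. It makes up 0.030/0.730 = 4.1% of the total at m = 10 and 0.0027/0.7027 = 0.4% at m = 112. Removing all of it leaves f = 0.70 and power Φ(2.828/0.8367 − 1.96) = 92.2%. The gain is about 1 point at m = 10 and about 0.1 point at m = 112.

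**3. Gain from adjusting for person-mean pre-cue craving.** The variance is multiplied by 1 − r², where r is the pre/post correlation of person means. The documents do not state r, so a range is assumed. At m = 14, with d held at 0.50:

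| Assumed r | 1 − r² | Power | Total N for 90% |
|---|---|---|---|
| 0 | 1.00 | 91.5% | 138 |
| 0.3 | 0.91 | 93.7% | 126 |
| 0.5 | 0.75 | 97.0% | 105 |
| 0.7 | 0.51 | 99.7% | 72 |

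Holding d fixed presumes no gender gap in background craving. If the 0.9 is already the SD of a reactivity score, the gain is nil.

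**4. What the gender main effect tests.** A simulation of 4,000 trials per scenario used 96 women and 48 men, 14 sessions per cue type and total SD 0.9. Assumed variance shares were 70% person, 15% session background and 15% residual. Rejection rates at the 5% level:

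| Scenario | Gender main effect, all cues | Post minus pre, smoking cues | Active minus neutral |
|---|---|---|---|
| Background gap 0.45, no reactivity gap | 91% | 5.0% | 5.7% |
| No background gap, reactivity gap 0.45 to smoking cues only | 39% | about 100% | about 100% |
| No gap of either kind | 4.5% | 5.3% | 4.7% |

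The simulation lets reactivity differ by gender but not between persons of the same gender, so the figures near 100% are optimistic. The contrast between columns in the first row does not depend on that.

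**5. Hypothesis 2.** The documents give no effect size or variance for the hormone models, only a blanket statement in C3i that power is at least 80%. No power figure for this hypothesis can be supported, with or without the rating.

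**The case against.** The plan is silent; it does not exclude the rating. Craving in Hypothesis 1 and cue-elicited craving in Hypothesis 2 could still be computed as change from the session start, as in the team's earlier work. This stands: the fault is a missing specification, not a decision to throw data away. The general covariate rule in C3j does not fill the gap, because it screens baseline characteristics for imbalance between groups and would not pick out a rating that varies from session to session.

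The design also has a second control. Neutral cues are in the model, and another earlier study described in C1 adjusted for neutral-cue responses. An active-minus-neutral gender contrast removes person-level background craving, as the simulation shows. This also stands, but it needs a gender-by-stimulus term, and none is listed. A random subject effect would not do the job, since it leaves between-person background craving in the gender comparison.

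Adjustment is not a pure gain in precision. Gender is not randomised, and hormones may themselves move pre-cue craving. Conditioning on the rating can change the question as well as the standard error.

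A reader might infer that the plan forfeits a large amount of power, by taking the 0.70 in C3i as the pre/post correlation. The documents do not support that. The 0.70 is the correlation among repeated measures within a participant, and C3i describes the measure as reactivity, so the SD of 0.9 may already be that of a reactivity score.

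**Conclusion.** The point holds as a gap in specification that should be closed; it is not a power shortfall. The rating is collected at every session, both Aim 1 hypotheses concern reactivity, and neither model says how the rating enters. As written, the Hypothesis 1 gender main effect does not isolate reactivity, and background craving that differs by gender would enter the estimate itself. In the simulated case this gave 91% rejections where reactivity did not differ, but that figure rests on the assumed 0.45 background gap and assumed variance shares.

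The effect on power is modest or uncertain: at most about 1 point from session swing, and about 2 to 8 points (93.7% to 99.7%, against 91.5%) from person-mean adjustment at assumed correlations of 0.3 to 0.7. The latter needs equal background craving in women and men and an SD of 0.9 that refers to craving, not reactivity. For Hypothesis 2 the concern is interpretive and cannot be sized.

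**What to change.** In C3j, for Aim 1:

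- Add the same session's session-start craving rating to the Hypothesis 1 mixed model and the Hypothesis 2 models, split into the person's mean and the session's deviation from it.
- Add the gender-by-stimulus-type term to Hypothesis 1, and say which coefficient tests the hypothesis.
- Keep presentation order, defined as first or second trial of the session, because one rating serves two cues and the first cue may carry over to the second.
- Report the models without the rating as a sensitivity analysis, for both hypotheses.

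This takes a few sentences and no new data. There are two costs. Sessions with a missing pre-cue rating drop out of the adjusted model. Adjusted and unadjusted estimates answer different questions, because gender is not randomised and hormones may affect pre-cue craving, so both must be shown and interpreted as such.
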